In addition, quantitative measure of hand opening area and closing force (QMHOc) will be conducted during the whole course of 12-week home-based practice, using pressure sensors (Pressure Profile Systems, Inc., Los Angeles, CA 90045) in conjunction with portable Moire Phase Tracking cameras (Metria Innovation, Inc., Wauwatosa, WI) (~1 hour).

F. Study Design and Methods

F.1. Lab-based testing

Each PT will be trained for the use of ReIn-Hand by watching a 20-min video, and practice the use of ReIn-Hand under the supervision of the research PT, [name], who is experienced in using ReIn-Hand device.

F.1.1. A. Pre-training non-EEG Experimental protocols

Once confirmed, a stroke participant will be randomly assigned to one of 11 physical therapists (10 clinical PTs+1 research PT (i.e., [name])) who will participate this study. The assigned PT will determine 1) the electrode positions for recording the muscle activities during performing different arm/hand function, and 2) the stimulation electrode positions and stimulation intensities for

achieving the best hand opening with the forearm at 0° and 90° positions (~1-1.5 hour). Then, the corresponding electrode positions will be marked, and the forearm/hand with these markers will be scanned (~0.5-1 hour). This visit is expected to last approximately 3 hours. The scanned results will be used to develop a subject-specific forearm-hand orthosis (FHO) that fits to the paretic forearm and hand.

B. Pre-training EEG Experimental protocols

Before and after this 12-week home-based practice, these stroke individuals will participate in an electroencephalography (EEG) experiment. Additionally, 10 control subjects will be recruited to participate in one session of this EEG experiment to provide healthy neuroimaging data for comparison.

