Throughout the experiment, we will measure scalp recordings using a 160-channel EEG system using active electrodes (Biosemi, Inc., Active II, Amsterdam, The Netherlands). Surface EEG electrodes will be mounted on a stretchable fabric cap based on the 10/20 system. The cap will be fitted on the head of the subject with the Cz electrode aligning with the intersection of the planes defined by the nasion, inion, and pre-auricular points. Eye movement detection electrodes will also be placed on the supra- and infra-orbital margins for detection of vertical eye movement. The skin under each electrode site will be prepared by clearing away any hair, and conductive gel

will be injected to achieve electrode impedances lower than $5\text{k}\Omega$ throughout the experiment. EEG data will be collected at 2048 Hz sampling rate and anti-aliasing filter (100 Hz) will be provided before data acquisition. The Biosemi system is equipped with active electrodes that provide a first amplification stage, allowing detection of EEG signals with a higher SNR and quicker preparation. A Polaris Krios handheld scanner and reflective markers (NDI, Ontario, Canada) will be used to record the EEG electrode positions compared to the coordinate system defined by the nasion, inion, and pre-auricular notches. EMG will be recorded from the extensor carpi radialis, flexor carpi radialis, and deltoid of the arm. The EEG and EMG data will be collected and stored on a computer.

These sessions will allow us to compare the cortical activity related to these movements pre- and post-intervention for the stroke individuals and how these compare to healthy controls to investigate any intervention-induced cortical reorganization.

F.1.2. The 1st and 2nd lab-based training with ReIn-Hand (2 visits)

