After the subject-specific FHO is ready, the stroke participant and his/her paired PT will be called to participate the 1st and 2nd lab-based training with ReIn-hand device. During these 2 visits, the assigned PT (1st test) or the research PT (2nd test) will train the stroke participant to use his/her FHO and the ReIn-Hand software on a mobile phone, until the stroke participant demonstrates the ability in using the device independently twice in a row. On the 2nd test, the research PT will also re-test partial of the clinical assessments, however, this time with the assistance of ReIn-Hand device. Each of these 2 visits is expected to last about 3 hours. During these 2 visits, we will measure the time for a stroke participant to learn the use of ReIn-Hand device. Within 0-3 days after the 1st (for PTs) or the 2nd lab-based training (for individuals with stroke), a 5min user survey to report the level of ease-of-use of the ReIn-Hand device will be conducted.

[figure not shown]

Figure 4. EEG Experimental setup showing a subject using the ACT^{3D} robot while high-density EEG and surface EMG signals will be simultaneously recorded. Visual feedback will be displayed on a computer screen.

F.2. Home-based practice

After the 3 lab-based visits as listed above, 4 out of 20 stroke participants will further participate the home-based practice. They will take the ReIn-Hand device, including his/her FHO, the mobile phone with ReIn-Hand software, and the electronic stimulator (300 PV, Empi, Minnesota, USA, a FDA approved clinical device) back to home. At home, they will perform 20 trials of pre-set tasks, like reaching and grasping, per session (1 hour), 1 session per day, 7 days per week for 12 weeks. During these 12 weeks, they will visit the lab once per week to make necessary device changes, update the partial of the clinical assessments, all without ReIn-hand. These clinical tests will also be re-measured at 1 and 3-month after the home-based practice, again without ReIn-hand.

Both electrodes and electrical stimulator are commercially available devices (300 PV Complete Electrotherapy System, Empi, Inc., St. Paul, MN). Each subject will be assigned task-specific, functional exercises targeted to their individual abilities, deficits, and personal preferences. Stimulation will be provided with the following characteristics:

Amplitude – at motor threshold with the maximum intensity lower than 100 mA
 Frequency – $50\pm20\%$ Hz

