 Pulse Duration – 300-400 microseconds
 Ramp/Fall Times and Duty Cycle – adjusted to the task

F.3. Data collection and procession

Main data collection is listed in table 2.

Day 1	#1, Demographic data, #2, Clinical assessments as listed above, #3, Time for a) determining the stimulation /recording electrode positions, b) for scanning,
Day 2	#1, EEG data, #2, EMG data, #3, finger position during hand-opening and graping force data during closing
Day 3	#1, Time for the stroke subject to a) to attach the FHO, b) use the software, including connecting all the cables following the instructions, c) set up the detection rule, and d) clean up. #2, The accuracy in detecting grasping and releasing; and #3, EMG data while performing task, sampled at 1K Hz.
Day 4	Measures #1-3 on Day 2, #4, ARAT and BBT with the assistance of ReIn-Hand.
Home-based test	Measures #1-4 on Day 3 and MAL-14, NSA, and hand opening and closing ability weekly during the 12-week home-based practice, then again at 1 and 3-month after. To the end of the 12-week home-based practice, we will use a GLOC scale (one question survey) to collect user overall satisfiaory level of the ReIn-Hand supported home practice.

Data analysis for evaluating the engineering aspects is listed on Table 3.

Primary measures	Measured by	Expectation
Time for learn-to-use the device	#1 on Day 3 and Day 4	<3 hours in each of the 2 days, and no difference between 2 days ¹ .
Time for setup and cleanup	#1 a) and d) on Days 3 & 4, and during the home-based test	<5 min for each, and significantly less than the

		measure #3 (a) on Day 1
Successful rate on controlling grasping and releasing during reaching	#2 on Days 3, 4, and during the home-based test	a false 'transfer' < 10%
Time delay caused by the device	We will detect the onset of EMG at the extensor measured on days 3 &4, and the onset of stimulation artifact. The latency between them will be calculated.	<350 ms
Difference in Clinical assessments with and without ReIn-Hand	Difference between measure #4 on Day 4 & measure #2 on Day 1	ARAT and BBT with ReIn-Hand will outperform that without ReIn-Hand.
Willingness to use ReIn-Hand at home	#1-3 during the home-based test	Continuous use on daily base.

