Cortical activity related to hand open with and without lifting	We will use EEG data to estimate the cortical activity related to the 2 motor tasks pre- and post-home-practice	Post-intervention cortical activity related to these 2 motor tasks become 'closer to' that in healthy control subjects.

¹Ease-of-use feature of the device will be reflected by the <3 hours learning time. We will further study effects of 1) PT's experience with ReIn-Hand, and 2) the number of experimental sessions on the time to learn to use the device. For PT's experience, since [name] already has 4-year experience in using current ReIn-Hand device in stroke participants, we will compare 1) the learning time on day 2 of the group 1 (N=10) working with the 10 PTs versus the time of the group 2 (N=10) working with [name]; and 2) the learning time of group 1 on day 2 with the 10 PTs versus the time of the same group on day 3 with [name]. A non-significant difference for both comparison will suggest non-significance for PT's experience in using the device. For the number of sessions needed to learn to use the device, we will compare the learning time of both groups on day 2 versus that on day 3. A non-significant difference will suggest sufficiency of one session in learning the device.

Evaluation of the usability of the ReIn-Hand: Within 0-3 days after Day 3, the 10 PTs and the 20 stroke participants will finish a 5min user survey to report the level of ease-of-use of the ReIn-Hand device. Items that will be rated (on ordinal scale 0-5, with the easiest use at 5) include: 1) determination of the stimulation/recording electrode positions (PT only), 2) setting up the initial detection rule (PT only), 3) fine adjustment of the detection rule (both), 4) placement of the FHO (both), 5) using the mobile phone software (both), 6) performance of the trained functional task (both). We expect to observe users' grades $\geq 4/5$, with grades $\leq 3/5$ will be queried for explanation and compiled for future design modifications.

Transportation: Participants will be given reimbursement for transportation expenses. Participants are encouraged to take public transportation, or to drive and park in Northwestern Medical School parking lots (located at [name] or [name]) where a parking sticker

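### The EEG row in Table 3 is listed as primary but has no defined index, distance or analysis; with 4 uncontrolled pre/post participants it can only be exploratory and descriptive

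*Protocol*

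**What the plan says.** Section F.3 introduces the table with "Data analysis for evaluating the engineering aspects is listed on Table 3". Its first column is headed as primary measures, and its last row is cortical activity for hand opening with and without lifting. The measurement is described as "We will use EEG data to estimate the cortical activity related to the 2 motor tasks pre- and post-home-practice", and the expectation column reads "Post-intervention cortical activity related to these 2 motor tasks become" closer to what the healthy controls show.

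Section F.1.1 B sets the timing: "Before and after this 12-week home-based practice, these stroke individuals will participate in an electroencephalography (EEG) experiment". It also says that "10 control subjects will be recruited to participate in one session of this EEG experiment", and it gives the aim of comparing sessions with each other and with controls as "to investigate any intervention-induced cortical reorganization".

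Section F.2 fixes how many people can have a post-practice session: "4 out of 20 stroke participants will further participate the home-based practice".

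The SAP covers survey scores, t-tests on satisfaction, and a repeated-measures ANOVA on hand function with the Box and Blocks Test as the main measure. EEG does not appear in it.

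**The concern.** Several other rows of Table 3 carry a usable yardstick: under 3 hours to learn, under 5 minutes for setup and for cleanup, under 10% false transfers, under 350 ms delay. The EEG row gives only a direction. Two sessions on the same person almost never give identical EEG values, so every participant ends up either nearer to or further from the controls even if nothing has changed. A direction alone cannot separate noise from effect.

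Two features of the design make this matter. The pre/post comparison rests on 4 people. And nothing in the design shows what a second session would look like 12 weeks later without practice: the controls are measured once, and no stroke participant is described as having repeat EEG without practice. A movement towards the controls could be session noise, familiarity with the task or an effect of practice, and the data could not tell these apart. Yet the row sits among the primary measures, and the stated purpose is to look into reorganization induced by the intervention.

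**Working it through.** The documents give no sample-size, power or error-rate figure for EEG, so there is no stated figure to reproduce.

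**Inputs**
- Participants with pre- and post-practice EEG: n = 4 (F.2 with F.1.1 B).
- Controls: 10, one session each (F.1.1 B).
- Tasks: 2 (Table 3).
- Assumption, not in the documents: with no true change, pre and post values are exchangeable, so the chance of ending closer to the control mean is p = 0.5.

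**1. Chance of moving closer with no true change**
- One participant: 50%.
- A simulation (200,000 runs; baseline separation of 0, 1 or 3 SD; session noise of 0.3 or 1 SD) gave 0.50 per participant in all six scenarios, and about 50% for the group mean.

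**2. Illustrative counts (the protocol states no such rule)**
- At least 3 of 4: 4p³(1−p) + p⁴ = 4/16 + 1/16 = 5/16 = 31.25%. The simulation gave 31.2% to 31.4%.
- All 4: p⁴ = 1/16 = 6.25%.

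**3. Both tasks, if independent**
- At least 3 of 4 on each: 0.3125² = 9.8%.
- All 4 on each: 0.0625² = 0.4%.
- Independence is doubtful, because the people, session and cap are the same. Positive correlation would raise both figures.

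**4. Sensitivity to p (drift or regression to the mean)**

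| p | At least 3 of 4 closer |
|---|---|
| 0.4 | 17.9% |
| 0.5 | 31.3% |
| 0.6 | 47.5% |
| 0.7 | 65.2% |

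**5. What a test on 4 pairs could do**
- Sign or signed-rank test: smallest two-sided p = 2 × (1/2)⁴ = 0.125.
- Paired t-test, 3 df: two-sided p < 0.05 needs mean change / SD > 3.182 / √4 = 1.59. For 80% power the true standardized change must be about 2.1.

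**6. Could Table 2 supply repeat EEG before home practice?**
Read literally, its Day 4 entry repeats Day 2 measures 1 to 3, the first of which is EEG. This looks like a numbering slip. Table 3 takes learning time, setup and accuracy from Days 3 and 4; the home-based row cites four measures on Day 3, where only three are listed; and the EEG session takes about 6 hours, against about 3 for that visit. Either way it adds no post-practice EEG beyond the 4.

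**The case against.** The strongest reply is that the row was never meant as a success rule. The column states an expectation, the table is introduced as an engineering evaluation, the wording in F.1.1 B is investigative, and the SAP gives the Box and Blocks Test as the main hand-function measure. This stands as far as it goes: EEG is not the trial's single primary endpoint. But it supports relabelling the row. As it stands, the row has primary status and no analysis.

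Four stronger readings are tempting, and the documents do not support them:
- **31% is the trial's false-positive rate.** It belongs to a count rule that the protocol does not contain. Other readings give about 50% (group mean), 6.3% (all 4) or, if both tasks are required and independent, 9.8% or 0.4%.
- **Two tasks give two chances.** Counting success on either task would give 1 − (1 − 0.3125)² = 53%, but the expectation is worded for both tasks together.
- **No group test could ever reach significance.** The 0.125 floor applies to the sign and signed-rank tests. A paired t-test has no such floor, and the SAP already uses t-tests elsewhere. Its limits are very low power and the absence of anything to attribute a change to.
- **The sponsor will report chance as reorganization.** The documents state a purpose, not a conclusion. The reference to mechanistic evidence in section D concerns preliminary data in 8 people, not this row.

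**Conclusion.** The point holds. A primary-listed measure has only a direction as its criterion, no index or distance, no analysis in the SAP, 4 people with pre/post data, and no repeat EEG without practice. With no true change, a participant or the group mean moves closer about half the time, so meeting the expectation is weak evidence of anything. This rests on exchangeability of pre and post; drift towards the controls would make it worse, and drift away would make it milder. The count figures are illustrations. Only a demand for all 4 on both tasks falls well below 5%, and no such rule is written. A paired t-test could detect a very large change, but no feature of the design would attribute that change to the device. The change should be made; it does not threaten the rest of the study.

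**What to change.** 1. Move the EEG row out of the primary measures in Table 3 and label it exploratory and descriptive. Say the same in the SAP.
2. Name one EEG index and one distance measure per task before any post-practice data are seen.
3. For each of the 4 participants, report pre and post values as scores against the 10 controls, using the Crawford-Howell t = (x − control mean) / (control SD × √(1 + 1/10)) on 9 df, together with the size of the change.
4. Make no group-level claim and no claim that practice caused reorganization.

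It would be natural to call a participant closer when the score crosses from outside to inside the controls' 95% prediction range (mean ± 2.262 × √1.1 = ± 2.37 SD). I advise against it. The range reflects spread between people, not session-to-session noise. Anyone who starts inside it can never count, and a move from 6 to 2.5 SD fails while one from 2.40 to 2.35 SD passes. In simulations with no true change, at least one of 4 crossed falsely in up to about 51% of runs under assumed noise and separation (for example, session noise of 1 control SD and a true position 3 SD from controls).

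Repeating the comparison at matched finger opening, which is recorded in the same session, is optional.

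The cost is wording in Table 3 and the SAP and a short analysis, with no added visit or recruitment. The downside is a more modest EEG statement.

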We plan to recruit about 100 moderately to severely impaired stroke subjects who have some shoulder and elbow control, but lack hand function (UE FMA Scores of 10-40/66, CMcM \leq 4) to participate in the cross-sessional experiments. Individuals with stroke will be selected from the Clinical Research Registry (CRR) housed at the ShirleyRyan AbilityLab which contains more than 700 members, as well as from stroke survivors residing in the Chicagoland area who wish to participate in the study. Recruitment of subjects who are currently enrolled in the Clinical Research Registry will be done via phone call and email. Recruitment of stroke survivors residing in the Chicagoland will be done via flyer or on-clinical-site survey for willingness of participation. In addition, in order to facilitate recruitment, we will post this study on The New Normal (TNN¹) Match matchmaking portal, a National Institutes of Health (NIH) funded collaborative project to give communities access to information about healthy research opportunities. These stroke subjects will go through 1 or 2 stages (i.e., the 1st stage as remote prescreening which is optional and the 2nd one as on-site screening for eligibility test which is required) of eligibility tests. Recruitment for stroke participants will be ended when 20 individuals with moderate to severe impairment post-stroke are enrolled and finished the data collection.

Once confirmed their desire and willingness to participate, the potential participant will be asked to sign an online e-Consent form, or a hard copy consent form. For individuals who signed the e-Consent form and passed the remote pre-screen, a hard copy of consent form will still be signed on the first on-campus visit.

We will recruit 10 healthy individuals at least 45 years old. These individuals will participate in one session of the EEG experiment, and will provide control data to compare against the stroke individuals who partake in the home-based practice.

¹ <https://www.nucats.northwestern.edu/news/2020/northwestern-new-normal-launch.html>.

Also, 10 independent physical therapists (PTs) or senior physical therapy students (SPTs), who have experience working with stroke subjects and using FES, will be recruited for setting up the ReIn-Hand device for stroke users, and then teaching stroke users to use the device. Stroke, PT and SPT users will provide feedback from clinicians and stroke users' angles, respectively.

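### The second PT-experience comparison of learning time changes training visit and trainer together, so it cannot isolate PT experience; the session comparison has the same problem if the groups are pooled

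*Protocol*

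**What the plan says.** Footnote 1 to Table 3 (Protocol F.3) plans two tests of whether PT experience affects learning time. The first compares group 1 (N=10, clinical PTs) with group 2 (N=10, research PT) at the first training visit. The second stays within group 1 and compares "the learning time of group 1 on day 2 with the 10 PTs versus the time of the same group on day 3 with" the research PT. The reading rule is "A non-significant difference for both comparison will suggest non-significance for" PT experience.

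For the number of sessions, the footnote says "we will compare the learning time of both groups on day 2 versus that on day 3", and takes non-significance to mean that one session is enough. It does not say whether the groups are pooled or analysed separately. Equality of the two days is also part of the expectation for learning time among Table 3's primary measures.

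Section F.1.2 fixes who trains when: "the assigned PT (1st test) or the research PT (2nd test) will train the stroke participant". Section F.1.1 adds an earlier step: "The assigned PT will determine 1) the electrode positions for recording the muscle activities during performing different arm/hand function". The assigned PT also sets the stimulation sites and intensities there, and the forearm is scanned with the positions marked to make the participant's orthosis. Table 2 includes this in the timing: "Time for the stroke subject to a) to attach the FHO".

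The SAP names t-tests for PT experience and number of sessions, but on participant satisfaction. It gives no analysis of learning time.

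**The concern.** Group 1 has a clinical PT at the first training visit and the research PT at the second. A drop in learning time between the visits may reflect practice, a more experienced trainer, or both, and this comparison alone cannot tell them apart. Practice is a plausible explanation: at the first visit participants train until they manage the device unaided twice in a row, and they are then timed again.

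Three things follow.

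- Because both comparisons must be non-significant, practice alone can prevent the conclusion that PT experience does not matter. The plan gives no reading for a significant or discordant result.
- If the session comparison is pooled, a trainer effect alone can make one session look insufficient. If it is run by group, its group 1 part is the same contrast as the second experience comparison, so one result would serve two conclusions.
- Session and trainer effects of opposite sign could cancel and hide a real trainer effect. The documents give no reason to expect a slower second visit, so this is the lesser risk.

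**Working it through.** There is no planned figure to reproduce: the documents give no SD, correlation, effect size or power for learning time. The check is of what each contrast estimates.

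**Notation.** S = first minus second visit. T = clinical minus research PT as trainer. F = clinical minus research PT as fitter; in group 1 it is present at both visits, because the same orthosis is used. m = mean for group 2 at the second visit. Effects are taken as additive, with no carryover.

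| | First training visit | Second training visit |
|---|---|---|
| Group 1 | m + S + T + F | m + F |
| Group 2 | m + S | m |

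**Contrasts.**

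- Comparison 1 (group 1 v group 2, first visit): (m+S+T+F) − (m+S) = F + T
- Comparison 2 (group 1, first v second visit): (m+S+T+F) − (m+F) = S + T
- Group 2 change: S
- Group 1 change minus group 2 change: (S+T) − S = T
- Session comparison pooled 10/10: [(S+T) + S]/2 = S + T/2

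These results need no assumed SD.

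**Illustrative size.** Assumed: SD 1 at each visit, 10 per group, within-person correlation ρ = 0.3 / 0.5 / 0.7, two-sided 5% t-tests, by simulation.

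*Joint rule met when T = F = 0:*

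| S (SD) | ρ = 0.3 | ρ = 0.5 | ρ = 0.7 |
|---|---|---|---|
| 0 | 91% | 91% | 90% |
| 0.25 | 87% | 85% | 81% |
| 0.5 | 74% | 67% | 53% |
| 1 | 32% | 18% | 4.5% |

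Comparison 1 alone is non-significant in 95% throughout. Hand check at ρ = 0.5, S = 0.5: the SD of the within-person difference is √[2(1−0.5)] = 1, so the noncentrality is 0.5√10 = 1.58. With 9 df the power is 0.293, and 0.95 × (1 − 0.293) ≈ 0.67. If the second-visit SD is 0.5, the rule is met in 67 / 60 / 50% at S = 0.5 and 16 / 9 / 3% at S = 1.

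*Session test when S = 0 and T = 1 SD:* if pooled, it is significant in 37 / 47 / 65% (48 / 57 / 68% with second-visit SD 0.5). In group 2 alone it stays at 5%.

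**Choice of model.** With F = 1 SD and S = T = 0, group 2's change and the difference in change both stay at 0. Generalised least squares with only visit and therapist type gives S = −0.35 / −0.25 / −0.15 and T = +0.70 / +0.50 / +0.30 SD, that is −(1−ρ)/2 and +(1−ρ). A model with group, visit and their interaction has no such bias.

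**The case against.** The strongest reply is that the harm is limited and conservative. Comparison 1 holds the visit constant and is already planned. A practice effect can only withhold the conclusion of no experience effect, since the footnote never says that a significant second comparison proves one. The under-3-hours criterion carries the ease-of-use claim, and these contrasts are introduced as further study. All of that is correct. It limits the finding but does not rescue comparison 2, which is offered as a test of PT experience and has a veto under the joint rule.

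The session point is conditional. If the comparison is run by group, group 2 already gives a clean estimate. That stands, and it is why the plan must say which is meant.

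The fitting effect can be called speculative: no document says that the fitter's experience alters learning time. Section E also defines the PT's role as "setting up the ReIn-Hand device for stroke users, and then teaching stroke users to use the device", so fitting plus training may be exactly what comparison 1 should measure. That reading is fair, and comparison 1 should be described that way. But the assigned PT's fitting does carry into the orthosis used at both visits, so an analysis that is safe against a fitting effect is preferable to one that assumes it away.

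The replacements have limits too. All experienced-PT data come from one therapist, so experience cannot be separated from that individual. The difference in change needs the no-carryover assumption. A session estimate from group 2 speaks only to participants taught by an expert.

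**Conclusion.** The concern holds. Comparison 2 estimates session plus trainer effect (S + T) and should not be read as a test of PT experience. The pooled session comparison, if that is what is meant, estimates S + T/2. Nothing in the SAP repairs either one.

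The confounding follows from the visit schedule alone. The percentages are illustrations that rest on the assumed SD, correlations and effect sizes, and on the 10/10 split in the footnote. With no PT effect, a practice gain of 0.5 SD lowers the chance of meeting the joint rule from about 90% to 53–74%, and a gain of 1 SD lowers it to 4.5–32%.

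Comparison 1 remains usable, and the under-3-hours criterion is untouched. This should be fixed: a planned inference is wrong as written, but the study is not invalidated.

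**What to change.** Amend footnote 1 and add the learning-time analysis to the SAP.

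1. **PT experience.** Make the first-visit group 1 v group 2 comparison the test, described as the effect of fitting plus training. Replace the group 1 before/after contrast with the between-group difference in change, labelled supportive. State its assumption: if first-visit training by a clinical PT shifts group 1's second-visit time by C, it estimates T − C.
2. **Session effect.** Estimate it from group 2's within-person change, or from a model with group, visit and their interaction. Do not pool the groups, and do not use a model with only visit and therapist type.
3. **Reporting.** Give estimates with 95% confidence intervals. Do not read non-significance as no effect or as proof that one session suffices.
4. **Clarifications.** Reconcile the footnote's day 2 / day 3 with Tables 2 and 3, which put learning time on Days 3 and 4. State how random assignment to one of 11 therapists yields 10/10: with equal probabilities the research PT would expect 20/11 ≈ 1.8 participants, and the group 2 estimate depends on having 10.

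**Cost.** Wording only, with no new data, but less precision. The 95% half-widths at ρ = 0.3 / 0.5 / 0.7, in SD units, are:

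| Estimate | Formula | Half-width |
|---|---|---|
| Session, group 2 alone | 2.262√[2(1−ρ)/10] | 0.85 / 0.72 / 0.55 |
| Session, interaction model (equal variances) | 2.101√[2(1−ρ)/10] | 0.79 / 0.66 / 0.51 |
| Session, pooled (confounded) | 2.093√[2(1−ρ)/20] | 0.55 / 0.47 / 0.36 |
| Difference in change | 2.101√[4(1−ρ)/10] | 1.11 / 0.94 / 0.73 |

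The difference in change would detect a 1 SD trainer effect only 43 / 56 / 78% of the time, so it can only support. The report should also say that the session estimate rests on 10 participants trained by one therapist, and that comparison 1 sets the clinical PTs against that same individual.

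### Non-significant differences in learning time, on 10 v 10, 10 pairs and 20 pairs, are read as no therapist-experience effect and as one session being enough, with no margin or interval

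*Protocol*

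**What the plan says.** Table 3 (Protocol F.3) lists time to learn the device among its primary measures. The expectation has two parts: under 3 hours on each of two days, and no difference between them. Footnote 1 adds three comparisons.

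- **Comparison 1:** first-visit learning time of group 1 (N=10, taught by the 10 PTs) against group 2 (N=10, taught by the research PT, who "already has 4-year experience in using current ReIn-Hand device in stroke participants").
- **Comparison 2:** group 1's first-visit time against "the time of the same group on day 3 with" the research PT.
- **Session comparison:** "we will compare the learning time of both groups on day 2 versus that on day 3", which gives 20 pairs.

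The rules are "A non-significant difference for both comparison will suggest non-significance for" the PT's experience and, for sessions, "A non-significant difference will suggest sufficiency of one session in learning the device".

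F.1.1 says each participant "will be randomly assigned to one of 11 physical therapists". F.1.2 says that "the assigned PT (1st test) or the research PT (2nd test) will train the stroke participant", and that training continues "until the stroke participant demonstrates the ability in using the device independently twice in a row".

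The SAP does not mention learning time. It names t-tests for therapist experience and number of sessions, but with satisfaction as the outcome. Neither document gives an alpha, SD, power, margin or interval for learning time.

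I read the footnote's days 2 and 3 as the first and second training visits, which are Days 3 and 4 in Tables 2 and 3. The numbering should be reconciled.

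**The concern.** Failure to reject is the only evidence the plan names for two positive conclusions: that therapist experience does not matter, and that one session is enough. A non-significant result from 10 or 20 people is compatible both with no difference and with a sizeable one. The rules also reward noise, since the more variable the times, the likelier the favourable reading.

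Both questions matter for a device meant for clinic and home. A moderate difference between newly trained therapists and the experienced one, or between visits, could be reported as none.

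The session rule has a further problem of meaning. If learning time is time to reach the independence criterion, a session that was well retained should make the second visit shorter. Equal times could mean that the participant had to learn the device again.

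**Working it through.** The plan states no power or sample-size figure for learning time, so there is nothing to reproduce.

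**From the documents:** 10 v 10, 10 pairs, 20 pairs; the therapist rule needs both of its comparisons to be non-significant.

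**Assumed:** t-tests at two-sided 0.05; normal data; equal SDs; an experience effect *d* that lengthens only group 1's first visit (no carry-over); a drop *s* in both groups at the second visit, in the same direction; within-person correlation ρ = 0.5, with brackets running from ρ = 0.7 to ρ = 0. Effects are in SDs of a single-visit time.

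**Expected differences.** Comparison 1: *d*. Comparison 2: *d* + *s*. Pooled session comparison: *s* + *d*/2, because only half the participants change therapist.

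**Single tests (noncentral t).** The noncentrality is *d*√(10/2) for comparison 1 and (difference/√(2(1−ρ)))√n for pairs. At ρ = 0.5, √(2(1−ρ)) = 1.

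- Comparison 1: power 18.5% at 0.5 SD and 39.5% at 0.8 SD, so it is non-significant 81.5% and 60.5% of the time. It has 80% power only at 1.32 SD.
- Comparison 2 with *s* = 0: power 29.3% and 61.6%, so non-significant 70.7% and 38.4%.
- Session rule, 20 pairs, *d* = 0: power 56.5% and 92.4%, so a true change is missed about 44% (22–68%) of the time at 0.5 SD and about 8% (1–33%) at 0.8 SD.

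**Therapist rule, both non-significant.** If the two tests were independent, *s* = 0 would give 0.815 × 0.707 = 58% at 0.5 SD and 0.605 × 0.384 = 23% at 0.8 SD. They share group 1's first visit, so the joint rate is higher. By simulation:

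| Second-visit drop *s* | True *d* = 0.5 SD called absent | True *d* = 0.8 SD called absent |
|---|---|---|
| 0 | 61% (48–71%) | 28% (13–46%) |
| 0.25 SD | 39% (20–60%) | 12–13% (3–34%) |
| 0.5 SD | 18% (4–45%) | 4% (0.3–22%) |

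**Precision of comparison 1.** The 95% half-width is t(18, 0.975) × √(1/10 + 1/10) = 2.101 × 0.447 = 0.94 SD. If group 1's SD is 1.5 times group 2's, Welch gives about 1.21 group 2 SDs.

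**Allocation.** Equal chances among 11 therapists would give the research PT 20/11 = 1.8 participants. The footnote needs 10.

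**The case against.** The best defence is that little hangs on these rules. The footnote says suggest, presents the comparisons as further study, and rests ease of use on the 3-hour limit. The therapist rule also requires two non-significant results, which cuts the false-null rate at 0.5 SD from 81.5% to 61% with no session effect. Some shortening at the second visit is plausible after training to a criterion, and the rate then falls to 39% or 18%. At 0.8 SD the session rule misses only about 8%. And with no SD in the documents, 0.5 SD might be a few minutes: at an assumed SD of 20 minutes it is 10.

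All of that stands and limits the severity. It does not supply what the rules lack. A 3-hour ceiling does not bound the difference between therapists or between visits, and Table 3 makes absence of a difference part of what is expected of a primary measure.

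A reader might also infer that the change of therapist between visits makes the stated conclusions wrong. Comparison 2 does mix therapist with session, and the pooled comparison absorbs half of any experience effect. But effects in the same direction add up and make non-significance less likely; they could mask each other only if they ran in opposite directions. The protocol draws no conclusion from a significant result, so the mixing corrupts no decision it states. It is a reason not to use comparison 2 as evidence on experience, and no more.

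**Conclusion.** The two non-significance rules are wrong as written and should be changed. A true 0.5 SD experience effect would be called absent about 61% of the time with no session effect, 39% with a 0.25 SD drop and 18% with a 0.5 SD drop; a true 0.5 SD session change would be missed about 44% of the time. These rest on assumed t-tests, normality, no carry-over and ρ = 0.5, and move widely with ρ. Carry-over works the other way from a session drop: if half the experience effect persisted to the second visit, the rates with no session effect would be about 74% at 0.5 SD and 52% at 0.8 SD.

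It would go too far to take 61% as the error rate of the plan, since it depends on there being no session effect, or to say that the ease-of-use claim fails. Nor is comparison 1 a measure of experience in general. Its experienced arm is one person, and the documents do not show how random assignment among 11 therapists produces 10 v 10.

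**What to change.** Replace both rules, and the expectation of no difference between days as judged by non-significance, with estimated differences and 95% confidence intervals in minutes, reported as descriptive.

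- **Therapist contrast.** Use comparison 1 with Welch's method, because variation between therapists enters group 1 only. Describe it as the 10 PTs against this one research PT. Claim no relevant difference only if the interval lies inside a margin set before the data are examined. Do not use comparison 2 as evidence on experience.
- **Allocation.** Reconcile F.1.1 with the 10 v 10 split in footnote 1. Call the contrast randomised only if allocation to the two groups was random.
- **Session change.** Report group 2, which keeps one therapist, separately from group 1. Do not infer sufficiency from similar times at the two visits. Judge it by the first visit: independent use twice in a row within 3 hours, which is already measured. State that learning time means time to this criterion, since Table 3 points instead to the component times in Table 2.
- **Keep** the 3-hour limit.

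This costs wording only, with no added participants, visits or measurements. The downside is that the therapist contrast will probably be inconclusive, with a half-width of about 0.94 SD. Even with a 90% interval and a true difference of zero, 10 v 10 would fall inside a 0.8 SD margin only about 12% of the time, and inside a 1.0 SD margin about 39%. The group 2 session estimate has a 95% half-width of t(9, 0.975)/√10 = 0.72 SD of the paired difference.
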